 2. Type of anesthesia will be decided depending upon the age and overall functioning of the participant. If the procedure is to be performed under general anesthesia (GA), GA consent will be obtained from the participant or guardian. Otherwise, monitored intravenous anesthesia (MIVA) will be performed after the consent.
- 475 3. In cases of MIVA anesthesia, peribulbar block will be injected in the operated eye.
- 476 4. The recipient eye that is to be operated on (i.e., the eye with LSCD) will be marked as such and the other eye will be covered.
- 478 5. Fluoroquinolone and proparacaine drops will be administered 3 times prior to the procedure.
- 4796. Peribulbar or retrobulbar block with 50:50 mixture of lidocaine and bupivacaine will be480 injected into the recipient eye.
- The participant will be brought to the operating suite and positioned in a supine positionunder the operating microscope in the manner typical for ophthalmic surgery.
- 483
 483
 484
 484
 484
 484
 484
 484
 484
 484
 484
 484
 484
 484
 484
 484
 484
 484
 484
 484
 484
 484
 484
 484
 484
 484
 484
 484
 484
 484
 484
 484
 484
 484
 484
 484
 484
 484
 484
 484
 484
 484
 484
 484
 484
 484
 484
 484
 484
 484
 484
 484
 484
 484
 484
 484
 484
 484
 484
 484
 484
 484
 484
 484
 484
 484
 484
 484
 484
 484
 484
 484
 484
 484
 484
 484
 484
 484
 484
 484
 484
 484
 484
 484
 484
 484
 484
 484
 484
 484
 484
 484
 484
 484
 484
 484
 484
 484
 484
 484
 484
 484
 484
 484
 484
 484
 484
 484
 484
 484
 484
 484
 484
 484
 484
 484
 484
 484
 484
 484
 484
 484
 484
 484
 484
 484
 484
 484
 484
 484
 484
 484
 484
 484
 484
 484
 484
 484
 484
 484
 484
 484
 484
 484
 484
 484
 484
 484
 484
 484
 484
 484
 484
 484
 484
 484
 484
- If excessive ocular surface bleeding is detected, topical epinephrine (1:10,000) will be used to constrict the blood vessels and minimize bleeding prior to or during the procedure. A conjunctival peritomy may be performed per investigator discretion. The fibrovascular tissue will be dissected from the limbus and the cornea. Hemostasis will be achieved by wet-field cautery. Mitomycin C may be placed underneath the conjunctiva per the surgeon's discretion.
- 10. The transwell with CALEC graft inside will be removed from the original container and will be
 placed on a sterile silicone platform and rinsed with BSS® Sterile Irrigation Solution. A freeheld trephine, size depending on the operated eye, will be used to punch the graft. The size

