- **Transplant** anticipated to occur 10 to 30 days after biopsy
- Day 1, Week 1, Week 2*, and Month 1 Visits
 - Same for Phase A and B participants
 - Only required for participants who complete a transplant
 - Visit schedule is timed from transplant date
- 832 Month 3, 6, 9*, 12, 15*, and 18 Visits
- 833 834

829

830

831

- Same for Phase A and B participants
 - Only required for participants who complete a transplant
 - Visit schedule is timed from transplant date

836

835

* The 2 week, 9 month, and 15 month visits will be optional for participants for whom travel is
prohibitive. For participants who opt out of these visits, the clinical site will work with the
participant's usual care ophthalmologist on the following:

- 840 (1) Advise that the participant follows the protocol's post-operative medication regimen, 841 although the regimen will not be enforced by the protocol in these participants.
 - (2) Request adverse events be reported to the clinical site, under a medical release from the participant.
- 844

842

843

845

846 6.8.1. STUDY SCREENING

847 Prospective participants, as defined by the inclusion/exclusion criteria, will be considered for 848 entry into this study. The study design and treatment regimen will be discussed with each 849 participant. Written informed consent will be obtained before any study-specific screening 850 evaluations are performed. The following evaluations and procedures will be performed for all 851 participants during the screening period:

852 853

857

858

861

- Informed consent process culminating in signed consent document
- Eligibility Assessment
- Record current ocular and systemic medications
- Record medical/surgical history in the past 5 years
 - Record demographic data, including date of birth, sex, and race/ethnicity
 - Review of systems
- Blood draw for testing for confirmation of eligibility criteria, including:
- 860 o Hepatitis B
 - Hepatitis C
- 862 o HIV, AIDS
 - CBC (including platelet and hemoglobin levels)

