959 Participants will be asked to report any pregnancies that occur within three days prior to 960 surgery. 961

962 6.8.8. CORNEAL RECONSTRUCTION WITH CALEC (DAY 0)

963 Participants will undergo corneal reconstruction within 24 hours of release of CALEC.

964	
965	A detailed description of the procedures can be found in Section 6.2.2. All participants will be
966	discharged the day of surgery, unless unforeseen complications prohibit discharge. If a
967	participant is admitted for observation, the Day 1 post-operative visit will occur while the
968	participant is in the hospital. All other visits will follow as originally scheduled.
969	
970	6.8.9. FOLLOW-UP PERIOD
971	Each participant will be followed for a period of 18 months from the time of the transplantation.
972	
973	Participants will be asked to report any pregnancies that occur within seven days after
974	transplant.
975	
976	6.8.10. POST-TRANSPLANT (DAY 1)
977	Slit lamp examination (both eyes) including
978	 Corneal opacification (as defined by Fantes Scale) (both eyes)
979	• Staining with fluorescein (extent of staining and epithelial defect area) (donor eye
980	required; recipient eye at discretion of investigator)
981	 Visual acuity (BCVA)(both eyes)
982	Intraocular pressure (both eyes)
983	Slit lamp photographs (both eyes) by certified technician, including
984	 Photography for neovascular area
985	• Photography (with fluorescein) for epithelial defect (donor eye required; recipient
986	eye at discretion of clinician)
987	 Punctal plugs, if needed (Section 6.5.5) (both eyes)
988	 Application of bandage contact lens, if needed (Section 6.5.5)
989	Adverse event assessment
990	
991	6.8.11. POST-OP FOLLOW-UP: WEEKS 1, 2, MONTH 1 (4 WEEKS ± 3 DAYS) AND
992	MONTHS 3, 6, 9, 12 (13, 26, 39, 52 WEEKS ± 1 WEEK), AND MONTHS 15, AND 18 (65 AND
993	78 WEEKS ±2 WEEKS)
994	 Symptom assessment (every visit except week 1, week 2, month 1)
995	 Slit lamp examination (both eyes) including
996	 Corneal opacification (as defined by Fantes Scale) (both eyes)
997	 Staining with fluorescein (extent of staining and epithelial defect area) (donor eye
998	required; recipient eye at discretion of investigator at week 1 and 2, and required at
999	month 1 and thereafter.)
1000	 Visual acuity BCVA (both eyes)
1001	Intraocular pressure (both eyes)
1002	 Slit lamp photographs (both eyes) by certified technician, including
1003	 Photography for neovascular area

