1.0 Study Objectives

The objectives of the "Safety and Feasibility of Cultivated Autologous Limbal Epithelial Cell (CALEC) Transplantation in the Treatment of Limbal Stem Cell Deficiency" study are as follows.

Excerpt from Protocol Section 2:

The main aim of the study is to preliminary estimates of the safety and feasibility of cultivated autologous limbal epithelial cell (CALEC) transplantation in the treatment of unilateral LSCD. Secondarily, efficacy of CALEC will be investigated and both safety and efficacy of CALEC will be compared to CLAU. These secondary objectives are intended to be exploratory rather than conclusive.

PRIMARY OBJECTIVES

- 1. Safety (within CALEC group): To establish the safety of CALEC transplantation by determining the incidence of primary ocular adverse events through 18 months of follow-up.
- 2. Feasibility (within CALEC group): To establish feasibility of manufacturing CALEC for corneal surface reconstruction.

SECONDARY OBJECTIVES

- 1. Safety (CALEC versus CLAU): To investigate whether CALEC is similar to standard treatment with CLAU by comparing incidence of primary ocular adverse events through 18 months of follow-up
- 2. Efficacy (within CALEC group): To investigate whether CALEC transplantation is efficacious in treatment of LSCD participants by comparing pre-operative to post-operative clinical parameters at months 3, 12, and 18.
- 3. Efficacy (CALEC versus CLAU): To investigate whether CALEC is similar to standard treatment with CLAU by comparing between-group changes from pre-operative to post-operative clinical parameters at months 3, 12, and 18.

STUDY CONCLUSIONS

The results of this Phase I/II study will provide guidance on whether to continue to a larger Phase III study and will also provide preliminary data to help determine sample size for future trials. Generally, if the study is not halted for feasibility issues, and there are no major safety or efficacy trends that favor CLAU, a larger study of CALEC could be considered. However, caveats of the study data and other potential factors outside of the trial will need to be considered and weighed in the ultimate decision of whether to proceed.

13 14

15

16

17

18

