2.0 Study Outcomes

20 21

Excerpt from Protocol Section 7:

22 23

PRIMARY OUTCOME MEASURES
SAFETY MEASURES

Safety will be assessed in both the CALEC and CLAU groups. The occurrence of the following adverse events at any time during the 18 months of follow-up in the recipient eye will serve as the **primary safety** events of interest:

- 1. Ocular infection (defined as endophthalmitis or microbial keratitis [bacterial, fungal, parasitic])
- 2. Corneal perforation
- 3. Graft detachment ≥50%

In addition to the primary safety events, all adverse events (systemic and ocular in donor and recipient eyes) will be captured. The severity of each adverse event and the relationship of the event to the cell therapy procedure will be assessed by an independent Medical Monitor(s) (MM). The independent Medical Monitor's (see Section 9.3) coding of the adverse event and designation of severity and relatedness to treatment will serve as final to use for adverse event reporting and safety outcome analysis.

FEASIBILITY MEASURES

Manufacturing feasibility will be evaluated in the CALEC group, for each biopsy attempt. At least one CALEC construct will be attempted to be manufactured from each biopsy, as detailed in the MOP. Each attempted construct will undergo Quality Control (QC) testing to determine product conformity to CMCF release criteria per MOP, which includes assessments of cell growth, cell viability, and culture contamination. If all of these QC release criteria are met for at least one CALEC construct, the biopsy attempt is considered a feasibility success.

In the event that a construct met all QC release criteria, but surgery was not performed for a reason unrelated to the development of construct for transplant, the case would still be considered a feasibility success for the biopsy attempt.

Up to two biopsy attempts of a single participant may be performed according to Section 5. Feasibility analysis will explore both the number of biopsies per participant and the number of construct attempts per biopsy, and whether those construct attempts met QC release criteria. Each of the individual QC testing and acceptance criteria will be documented to further describe constructs that did not meet the criteria for release.

SECONDARY OUTCOME MEASURES

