5.0 Statistical Analysis Plan

Safety Analysis

 Coding of all adverse events for analysis will be based on the MedDRA coding determined by the Medical Monitor. The following safety analyses will be performed.

1. Primary Safety Analysis (within-CALEC group evaluation of primary safety outcomes):

- a. The primary safety events of interest (ocular infection, corneal perforation, and graft detachment >=50%) in the recipient eye will be summarized as the numbers and percentages (and 95% exact confidence intervals) of participants having each event and the number and percentage (and 95% exact confidence intervals) of participants having any of the three events, up to 18 months.
 - These events will be evaluated in CALEC Group Phase A and Phase B participants combined. Only participants who completed transplant and only events occurring after transplant will be included.

2. Primary Safety Analysis (CALEC versus CLAU comparison of primary safety outcomes):

- a. The primary safety events of interest (ocular infection, corneal perforation, and graft detachment >=50%) in the recipient eye will be summarized as the numbers and percentages (and 95% exact confidence intervals) of participants having each event and the number and percentage (and 95% exact confidence intervals) or participants having any of the three events, up to 18 months
 - i. These events will be evaluated within each treatment group, in Phase B participants only. All participants who were randomized will be included regardless of whether transplant was completed. Phase B participants who discontinued prior to randomization will not be included. All events occurring after randomization will be included. Events prior to randomization will not be included.
- b. The two treatment groups will also be compared by computing the differences in percentages (and 95% exact confidence intervals) having each event and the difference in percentages (and 95% exact confidence intervals) having any of the three events.
- 3. Secondary Safety Analysis (explore/evaluate all adverse events): All reported adverse events up to 18 months (including systemic, recipient, and donor eye events) will be evaluated as follows.

- a. Within each MedDRA system organ class, tabulate the number and percentage of participants having at least 1 event within the given system organ class. Evaluate both of the following ways:

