 - i. Within-CALEC group: Evaluate in CALEC Group Phase A and Phase B participants combined. Only participants who completed transplant will be included. Only events occurring after transplant will be included.
 - ii. CALEC versus CLAU comparison: Evaluate within each treatment group, in Phase B participants only. All randomized participants will be included regardless of whether transplant was completed. Phase B participants who discontinued prior to randomization will not be included. All events occurring after randomization will be included. Events prior to randomization will not be included.
- b. Within each adverse event term (MedDRA lower level term), tabulate the number of events and number of participants with at least 1 event, separately for systemic, recipient eye, and donor eye events. Evaluate the data in both of the following ways:
 - Within-CALEC group: Evaluate in CALEC Group Phase A and Phase B participants combined. Only include participants who completed transplant and only include events occurring after transplant.
 - ii. CALEC versus CLAU comparison: Evaluate within each treatment group, in Phase B participants only. All participants who were randomized will be included regardless of whether transplant was completed. Phase B participants who discontinued prior to randomization will not be included. All events occurring after randomization will be included. Events prior to randomization will not be included.
- 4. Additional Safety Analyses for DSMC Monitoring Purposes Only:
 - a. The mean number of events per patient will be calculated as the total number of events reported in the treatment group, divided by the total number of patients in the treatment group. Evaluate the data in both of the following ways:
 - i. Within-CALEC group: Evaluate in CALEC Group Phase A and Phase B participants combined. Include only participants who completed transplant and include only events occurring after transplant.
 - ii. *CALEC versus CLAU comparison*: Evaluate within each treatment group in Phase B participants only. All participants who were randomized will be included regardless of whether transplant was completed. Phase B participants who discontinued prior to randomization will not be included. All events occurring after randomization will be included. Events prior to randomization will not be included.

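### The within-CALEC primary safety analysis drops a transplant operation abandoned because of a corneal perforation, and does not define when event counting starts

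*SAP*

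**What the plan says.** - **Objective** (SAP 1.0, matching Protocol 2.1): "To establish the safety of CALEC transplantation by determining the incidence of primary ocular adverse events through 18 months of follow-up".
- **Primary events** (SAP 2.0, matching Protocol 7.1.1): "The occurrence of the following adverse events at any time during the 18 months of follow-up in the recipient eye". The three events are ocular infection, corneal perforation and graft detachment of at least 50%.
- **Analysis set and event window** (SAP 5.0, item 1.a.i): "Only participants who completed transplant and only events occurring after transplant will be included".
- **Secondary adverse-event tables, within CALEC** (SAP 5.0, item 3.b): "Only include participants who completed transplant and only include events occurring after transplant". The system-organ-class table (3.a) and the mean event count for the DSMC (4.a) carry the same limit.
- **Phase B comparison with CLAU** (SAP 5.0, item 2): all randomized participants, whether or not transplant was completed, and "All events occurring after randomization will be included". Protocol 12 records that the CLAU comparison has since been discontinued.
- **The operation** (Protocol 6.2.2.2): before the graft is punched out and placed, "The fibrovascular tissue will be dissected from the limbus and the cornea".
- **Follow-up**: Protocol 6.8.9 states "Each participant will be followed for a period of 18 months from the time of the transplantation". In Protocol 6.8 the post-transplant visits are "Only required for participants who complete a transplant".

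**The concern.** The objective is the safety of a procedure. Part of that procedure is surgery on the recipient cornea before any graft is on the eye, and perforation of that cornea is a primary event. An analysis set defined by completion of the transplant depends on how the operation went. If a perforation is the reason the operation stops, the event removes its own participant from the analysis.

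At stake is the headline safety estimate, which Protocol 2.3 says will help guide whether to go on to Phase III. With about 17 participants and an expected rate near 5% (SAP 3.0), one event more or less is the difference between reporting none and reporting the whole expected rate.

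**Working it through.** **1. The plan's own figures.** SAP 4.0 gives exact binomial 95% intervals for n = 15. With no events the upper limit is 1 − 0.025^(1/n). For n = 15 this is 21.8%, and the SAP prints 22%. For 1/15 the exact interval is 0.2% to 31.9%, and the SAP prints 0 to 32%. The probability of at least one event is 1 − (1 − p)^n. At p = 5% and n = 15 it is 1 − 0.95^15 = 0.54, as printed. The plan's interval method is therefore the one used below.

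**2. The two filters of item 1.a.i applied to three cases.**

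| Case | Completed transplant? | Event after transplant? | Result |
|---|---|---|---|
| Perforation on Day 1 or later, graft in place | Yes | Yes | Counted |
| Perforation during the dissection, graft still placed | Yes | Not defined | Depends on the reader |
| Perforation during the dissection, operation abandoned | No | No transplant to be after | In neither numerator nor denominator |

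The third row needs no interpretation. The restricted within-CALEC tables do not recover it. The Phase B comparison would have counted it for randomized participants, but never covered Phase A and is discontinued. By contrast, Protocol 15.7.1 summarizes safety events from the biopsy onward for a second CALEC transplant, a window that contains the second operation.

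**3. Size for one abandoned case.** Protocol 5.5 ends enrollment at 17 completed transplants, unless the timeline ends it sooner. Only completed transplants count towards 17, so an abandoned case can be replaced. Assume one abandoned case with perforation and no other primary event.

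- Plan: 0/17 = 0%; upper limit 1 − 0.025^(1/17) = 19.5%.
- Operations begun: 1/18 = 5.6%. The lower limit is 1 − 0.975^(1/18) = 0.1%. The upper limit solves (1 − p)^18 + 18p(1 − p)^17 = 0.025, giving p = 27.3%.

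Variants:
- Timeline ends before the case is replaced: 0/16 (0 to 20.6%) against 1/17 = 5.9% (0.1 to 28.7%).
- SAP planning size: 0/15 (0 to 21.8%) against 1/16 = 6.25% (0.2 to 30.2%).
- Graft still placed, strict reading of the window: 0/17 (0 to 19.5%) against 1/17 = 5.9% (0.1 to 28.7%).

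For scale, the expected number of participants with an event is 0.05 × 17 = 0.85.

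**4. Chance of seeing an event.** The documents do not say what share of the 5% risk is operative. Let f be that share, and suppose that no operative event is counted. The probability of at least one counted event is then 1 − (1 − 0.05(1 − f))^n.

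| f | n = 15 | n = 17 |
|---|---|---|
| 0 | 0.54 | 0.58 |
| 25% | 0.44 | 0.48 |
| 50% | 0.32 | 0.35 |

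The f values are assumptions that show a range.

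**The case against.** **The rule may only be meant to set aside the biopsy and manufacturing period.** Protocol 6.8.8 labels the operation Day 0, Protocol 6.8 times visits from the transplant date, and follow-up runs from the time of transplantation. Where the Protocol wants to leave out the day of a procedure it says so, as with the second biopsy in 15.7.1; item 1.a.i has no such exclusion. This stands for the second row of the table. A reader might infer that every intraoperative perforation drops out, but the documents do not settle that when the graft is placed. It does not help the abandoned case, which fails the completion filter whatever the window.

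**The event would not be hidden.** This also stands. The note to the SAP Appendix has all adverse events after baseline collected and reported in every scenario. Protocol 9.2 sends all events to the Medical Monitor and the DSMC, Protocol 7.3 tabulates all reported events, and the SAP flow chart accounts for all participants. The loss is from the primary result and the within-CALEC tables, not from surveillance.

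**No such event is documented.** Correct. A reader might infer that the primary rate is biased towards zero. That holds only if such an event occurs; nothing in the documents shows that any of the expected 5% is operative.

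**Participants who received the graft are a coherent population for an exploratory study.** They are, and their result is worth showing. For a procedure's safety, though, it should not be the only primary result.

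**Conclusion.** The point holds in a limited form. Item 1.a.i excludes a participant whose recipient-eye operation was begun and then abandoned because of a corneal perforation, and it leaves open whether a perforation during a completed operation counts. One abandoned case would move the primary estimate by 5.6 percentage points and its upper limit by 27.3 − 19.5 = 7.8 points. This rests on two assumptions: that one such case occurs, with no other primary event, and that enrollment still reaches 17 completed transplants. The Protocol and SAP agree on the endpoint and the SAP's intervals are right, so this is a gap in the analysis set and event window. It is neither a contradiction nor a calculation error. It mainly concerns perforation, since graft detachment requires a graft.

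**What to change.** Reword SAP 5.0 item 1.a.i as follows.

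- For ocular infection, corneal perforation and the any-event composite, the denominator is every participant in whom the recipient-eye transplant operation (Protocol 6.2.2.2) was begun. Events count from the start of that operation through 18 months.
- For graft detachment, the denominator stays at participants with a graft placed. Otherwise an abandoned case would dilute that rate; one detachment would read 1/18 = 5.6% rather than 1/17 = 5.9%.
- Intraoperative events and abandoned operations are listed on their own lines.
- The completed-transplant set is shown as supportive.

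**Cost.** The operative events are already collected, so no new operative data are needed, but the change takes more than one sentence. Abandoned cases have no scheduled 18-month follow-up: the post-transplant visits apply only after a completed transplant, and the nearest provision, Protocol 5.7, gives 30 days of monitoring for biopsy-related events, extended for an unresolved donor-eye complication. The SAP should report these cases with the follow-up available and say that it is incomplete. The change can also move the rate down: an operation abandoned for an unrelated reason would enter as event-free and slightly lower it.
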